[Part 2 of 2 of the document. The other parts are not shown.]

The start of the study is defined as the date the first enrolled subject signs an Informed Consent Form (ICF). The point of enrollment occurs at the time of subject number allocation. The end of the study is defined as the date of the last subject's last assessment (scheduled or unscheduled).

3.3. Additional Groups

Following review of the safety, tolerability, PK, and PD data (where systemic exposure is not expected to exceed that stated in the dose escalation stopping criteria [[Section 3.7](#)]), additional dose groups may be added to the study. The maximum dose for any additional group will not exceed 20 µg. Up to 3 further groups of 8 subjects (6 active: 2 placebo) may be included in Part A, and up to 3 additional groups of 8 subjects (6 active: 2 placebo) may be included in Part B. The requirement for additional groups will be agreed with the Sponsor and documented in the Trial Master File (TMF).

3.4. Discussion of Study Design, Including the Choice of Control Groups

For both parts of the study, a sequential-group, ascending-dose design has been chosen for safety reasons as OLP-1002 is in the early stages of clinical development, with Part A of the study being the first time it will be administered to humans. Subcutaneous doses have been chosen for both parts of the study, as this is the intended clinical route of administration.

In Part A, safety data up to Day 10 will be reviewed prior to dose escalation, and PK data up to Day 7 will be reviewed for all groups receiving ≥ 12 µg OLP-1002. In Part B, safety,

tolerability and PK data up to Day 22 will be reviewed for all dose groups. As the $t_{1/2}$ of OLP-1002 is predicted to be approximately 180 hours (based on non-clinical data) review of safety data up to Day 10 (Part A) and Day 22 (Part B) is considered sufficient to ensure data from at least one half-life is included in the review. In addition, as plasma exposures are anticipated to be low, it is expected that it will only be possible to perform an assessment of peak concentrations (C_{max}) and therefore PK data to Day 7 (Part A) and Day 22 (Part B) will be sufficient. Additionally, a cumulative safety review will occur such that additional emerging safety data from earlier groups will be considered when making a dose escalation decision.

Healthy male and female subjects will be recruited into this study. The inclusion of females of childbearing potential is in accordance with International Council for Harmonisation (ICH) M3, based on the short dosing duration (< 2 weeks).

In Part A, it is anticipated that groups of 4 subjects (3 active: 1 placebo) will be sufficient in order to determine safety and tolerability. In order to assess the PD effects of OLP-1002, 3 groups in Part A will include 8 subjects (6 active; 2 placebo). A full review of the safety and tolerability data from Part A will be performed to determine the dose regimen for Part B. Part B may start after a full review of all safety and tolerability data from Group A1 to A6. A review of PD data may also be performed, at the discretion of the Investigator. Details of the dosing regimen and duration used for Part B of the study will be documented in the TMF.

Based upon the nonclinical data, the duration of a 28-day follow-up in Part A, and a 57-day follow-up in Part B is considered adequate to achieve the study objectives.

Pharmacokinetic analysis in Part A will initially only be conducted for groups receiving $\geq 12 \mu\text{g}$ OLP-1002, with retrospective analyses of samples from lower dose groups occurring in the event of PK data being quantifiable at doses $\geq 12 \mu\text{g}$ and if supported by bioanalytical stability data. Dose escalation decisions for doses $< 12 \mu\text{g}$ in Part A will not require PK data. The rationale for this is that maximum plasma concentrations at $12 \mu\text{g}$ are expected to be approximately 0.078 ng/mL and the bioanalytical method used for preclinical species has a lower limit of quantification (LLOQ) of 5 ng/mL. The increased sample volume possible from humans (compared to small animals) may afford an approximate 10-fold increase in sensitivity with possibly an additional 5-fold increase from the use of a more sensitive mass spectrometer. This could potentially deliver an LLOQ of around 0.1 ng/mL. Therefore, even with the increased assay sensitivity plasma levels from doses at or below $12 \mu\text{g}$ are not expected to be quantifiable. It is apparent from the predicted plasma concentrations (see [Section 3.5.2](#)) that only a small number of samples around C_{max} at the highest dose would be quantifiable and that a conventional approach to pharmacokinetic will not achieve a full definition of the plasma concentration vs time profile or enable an estimation of the terminal phase. In addition the planned dose levels have a high safety margin when comparing the predicted exposures to the exposures at the NOAEL (see [Section 3.5.2](#)), with the $12 \mu\text{g}$ dose level having an expected 312-fold and 255-fold safety margin based on C_{max} and $AUC_{0-\infty}$, respectively. Therefore, if exposure is significantly higher than predicted it is not expected to exceed the PK stopping criteria.

This study will be double-blind and placebo-controlled in order to avoid bias in the collection and evaluation of data during its conduct. Placebo has been chosen as the control treatment to assess whether any observed effects are treatment-related or simply reflect the study conditions.

Conducting the study in healthy subjects mitigates the potential confounding effects of the disease state and concomitant medications.

Continuous ECG monitoring will be recorded in this study and archived for potential future analysis of OLP-1002 effects on the QT interval, with a view of supporting a potential thorough QT study waiver.

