3.6. Dose Escalation

In Part A, doses will be administered in an escalating manner following satisfactory review by the Sponsor and Investigator of the safety, and tolerability data up to Day 10 (216 hours postdose) from groups that received lower doses of OLP-1002. For escalation to doses > 12 µg, PK data up to Day 7 (144 hours postdose) will also be reviewed. All available safety, tolerability, and PK data from previous groups will be reviewed prior to dose escalation.

In Part B, doses will be administered in an escalating manner following satisfactory review of safety, tolerability, and PK data up to Day 22 (216 hours post-final dose) from groups that received lower doses of OLP-1002. Doses may be reduced and may be lower than the starting dose. Available safety, tolerability, and PK data from all previous groups will be reviewed prior to dose escalation.

Dose escalation in Part A will only occur if data from a minimum of 4 subjects (Groups A1, A3, A5, A7, and A8) or 6 subjects (Groups A2, A4, and A6) have been reviewed from the previous lower dose group, such that data from a minimum of 3 or 4 subjects, respectively, who have received OLP-1002 will be used to make the dose-escalation decision. Dose escalation in Part B will only occur if data from a minimum of 6 subjects have been reviewed from the previous lower dose group, such that data from a minimum of 4 subjects who have received OLP-1002 will be used to make the dose-escalation decision.

The justification for this is as follows:

- The study drug is of a known pharmacological class for which the on-target effects in humans are well characterized. Based upon nonclinical data, no clinically important off-target effects are expected within the proposed dose range.

- A minimum of 3 subjects receiving the active drug is considered sufficient to characterize the safety profile for OLP-1002.

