3.7. Dose Escalation Stopping Criteria

In Parts A and B, following consultation with the Sponsor, dose escalation will be stopped if:

- Clinically relevant signs or symptoms of similar nature occur in 2 or more subjects in a group that, in the opinion of the Investigator, warrant stopping of dose escalation.
- One or more subjects experience an SAE that is considered to be related to OLP-1002.
- Two or more subjects in the same group experience severe non-serious AEs (ie. severe non-serious AEs considered as, at least, possibly related to OLP-1002 administration), independent of whether the AEs are within or not within the same system organ class.
- There is evidence of clinically significant increases in aspartate aminotransferase, alanine aminotransferase or alkaline phosphatase (defined as 3 times the upper limit of normal), or total bilirubin (defined as 2 times the upper limit of normal) that are considered to be related to OLP-1002 in 2 or more subjects in a group. Results will be confirmed with repeat testing.
- QT interval corrected for heart rate using Fridericia's method (QTcF) increases > 60 msec compared to baseline (predose for Part A or Day 1 predose for Part B) and/or absolute QTcF values > 500 msec (confirmed by repeat measurement) in 2 or more subjects in a group.
- Tachycardia (> 150 beats/min) in the resting supine position (confirmed by 2 repeat measurements) on at least 1 occasion within a 24-hour interval in ≥ 1 subject in a group.
- Severe hypertension (systolic blood pressure > 180 mmHg and/or diastolic blood pressure > 110 mmHg) in the resting supine position (confirmed by 2 repeat measurements) on at least 1 occasion within a 24-hour interval in ≥ 1 subject in a group.
- The dose will not exceed 20 μg or the systemic exposure for any individual subject is predicted to exceed a C_{max} of 24.9 ng/mL (plasma) and/or an AUC_{0-24} of 128 ng/mL; i.e., systemic exposure will be no greater than the NOAEL in the most sensitive species (100,000 pmol/kg in rat [462 $\mu\text{g}/\text{kg}$]).

If the sponsor deems it appropriate to resume dosing after the internal safety review, it can be done after the approval of a substantial protocol amendment.

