Appendix 6: Schedule of Assessments

Study Plan – Part A (Single Dose)

	Pre-screening ^d	Screening	Day -2	Day -1	Days 1 to 3	Day 4	Day 7 (± 2 days)	Day 10 (± 2 days)	Day 14 (± 2 days)	Poststudy (Day 28 ± 2 days)
Inclusion/exclusion criteria		X								
Demographic data		X								
Medical history		X								
Urine drugs of abuse screen		X	X							
Alcohol breath test		X	X							
Cotinine test		X	X							
Serology		X								
Hormone panel		X								
Urine pregnancy test ^a		X	X							X
Informed consent	X	X								
Study residency:										
Check-in			X							
Check-out					Day 3 (48 hours postdose)					
Non-residential visit	X	X				X	X	X	X	X
Study drug administration:					Day 1 (0 hours)					
Safety and tolerability:										
Adverse event recording		X	X	X	Ongoing	X	X	X	X	X
Concomitant medication recording		X	X	X	Ongoing	X	X	X	X	X
Supine blood pressure, pulse rate, respiratory rate, and body temperature		X			Predose, 1, 2, 4, 8, 24 (± 1 hour), and 48 hours postdose	X	X	X	X	X

	Pre-screening ^d	Screening	Day -2	Day -1	Days 1 to 3	Day 4	Day 7 (± 2 days)	Day 10 (± 2 days)	Day 14 (± 2 days)	Poststudy (Day 28 ± 2 days)
Supine 12-lead ECG		X			Predose, 4, 24 (± 1 hour) and 48 hours postdose		X		X	X
Continuous ECG extraction ^{b,c}				-24, -23.5, -23, -22.5, -22, -21.5, -21, -20, -18, -16, -12 hours	Day 1: Predose, 0.5, 1, 1.5, 2, 2.5, 3, 4, 6, 8, 12 and 24 hours					
Heat pain threshold test (heat pain threshold and heat pain tolerance)					Day 1: predose, 2, 4, 12, and 24 hours postdose (± 1 hour)					
Clinical chemistry, haematology, and urinalysis		X	X		48 hours postdose		X		X	X
Height and BMI		X								
Body weight		X	X							X
Physical examination		X								
Symptom-directed physical examination					Prior to discharge		X		X	X

	Pre-screening ^d	Screening	Day -2	Day -1	Days 1 to 3	Day 4	Day 7 (± 2 days)	Day 10 (± 2 days)	Day 14 (± 2 days)	Poststudy (Day 28 ± 2 days)
Injection site assessment					Predose, 1, 2, 4, 8, 24, 48 hours postdose		X		X	X
Pharmacokinetics^e										
Blood sampling					Predose, 0.5, 1, 1.5, 2, 3, 4, 6, 8, 12, 16, 24, 36 and 48 hours postdose	X	X	X	X	X
Pharmacodynamics^d:										
Intradermal capsaicin test (capsaicin-evoked pain and secondary hyperalgesia measurement)	X		X		Day 2 (The area of secondary area of hyperalgesia will be evaluated at 5 and 30 minutes post-capsaicin injection)					

Abbreviations: BMI = body mass index; ECG = electrocardiogram.

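### Part A escalation review is said to ensure one half-life (about 180 h) of safety data, but laboratory and ECG data nominally stop at Day 7 (144 h, 0.80 half-life)

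*Protocol*

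**What the plan says.** Section 3.4 predicts a human half-life of about 180 h from non-clinical data. From this it argues that a safety review up to Day 10 in Part A, and up to Day 22 in Part B, "is considered sufficient to ensure data from at least one half-life is included in the review".

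Section 3.6 makes escalation in Part A depend on safety and tolerability "data up to Day 10 (216 hours postdose) from groups that received lower doses of OLP-1002". The same section gives the hour count for Day 7: "PK data up to Day 7 (144 hours postdose) will also be reviewed".

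Section 3.7 lists the criteria that stop escalation. One reads in part "There is evidence of clinically significant increases in aspartate aminotransferase, alanine aminotransferase or alkaline phosphatase" and also covers total bilirubin; another is based on QTcF. Both need findings in two or more subjects in a group.

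In the Part A schedule of Appendix 6, the Day 10 visit has a ±2-day window. It carries adverse events, concomitant medication, vital signs and a PK sample. The 12-lead ECG row gives "Predose, 4, 24 (± 1 hour) and 48 hours postdose" and then marks Day 7, Day 14 and Day 28. The row for "Clinical chemistry, haematology, and urinalysis" has 48 h, Day 7, Day 14 and Day 28 after dosing. Injection-site assessment and symptom-directed examination are likewise marked at Day 7 and Day 14. None of these four rows has a mark at Day 10.

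**The concern.** Section 3.4 attributes a specific property to the escalation review: it is sure to contain at least one half-life of follow-up. Someone reading Sections 3.4 and 3.6 alone would take it that liver tests and QTcF are judged on 216 h of data. The schedule supplies those data only from a visit nominally 72 h earlier (216 − 144 = 72).

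The liver-test and QTcF criteria can be judged only on laboratory and ECG results, so the shortfall falls on the data they use. It can arise at each of the seven escalation steps between Groups A1 and A8 of a first-in-human study. Section 3.4 also says that exposure at or below 12 µg is not expected to be quantifiable, so at most of those steps the clinical safety data carry the decision.

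**Working it through.** **Inputs.** Half-life 180 h (Section 3.4). Dosing at 0 h on Day 1 in Part A; final Part B dose on Day 13; visit days and ±2-day windows (all Appendix 6). Stagger between subjects (Section 3.4.1).

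**Formulas.** Part A hours postdose = (Day − 1) × 24. Part B hours after the final dose = (Day − 13) × 24. Coverage = hours / 180.

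**The plan's own figure.** Day 10: (10 − 1) × 24 = 216 h; 216/180 = 1.20. The nominal statement is reproduced for data collected at that visit.

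**Coverage by visit.**

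| Visit | Day | Hours | Half-lives |
|---|---|---|---|
| Part A Day 10 (adverse events, vital signs), earliest | 8 | 168 | 0.93 |
| nominal | 10 | 216 | 1.20 |
| latest | 12 | 264 | 1.47 |
| Part A Day 7 (laboratory, ECG, injection site), earliest | 5 | 96 | 0.53 |
| nominal | 7 | 144 | 0.80 |
| latest | 9 | 192 | 1.07 |
| Part A Day 14 (next laboratory, ECG, injection site), earliest | 12 | 264 | 1.47 |
| nominal | 14 | 312 | 1.73 |
| Part B Day 22, earliest | 20 | 168 | 0.93 |
| nominal | 22 | 216 | 1.20 |

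**Are the empty Day 10 cells real?** Appendix 3 allows six laboratory samples in Part A. Screening, Day -2, 48 h, Day 7, Day 14 and Day 28 make six, so a Day 10 sample would be a seventh. Appendix 3 also allows 19 PK samples: 14 from predose to 48 h, plus Days 4, 7, 10, 14 and 28, which is 19. The columns therefore read correctly.

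**Effect of the stagger.** In a 4-subject group, when the last two subjects reach 216 h, the second is at 216 + 48 = 264 h (Day 12) and the first at 216 + 96 = 312 h (Day 14). In an 8-subject group the two sentinels are at 216 + 48 = 264 h (Day 12). So the first subject of four may have Day 14 results. The second of four, and both sentinels, may have them only if that visit is held at its earliest limit. The other 2 of 4, or 6 of 8, have laboratory and ECG results no later than the Day 7 visit. In an 8-subject group, with one active and one placebo sentinel, those six include 5 of the 6 subjects on active drug (6 − 1 = 5).

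**Sensitivity to the half-life.** Section 3.5.2 scales the monkey half-life of 84 h from 3.1 kg to 60 kg with exponents 0.75 and 1: 84 × (60/3.1)^0.25 = 176 h. With 176 h, coverage is 144/176 = 0.82 at Day 7 and 168/176 = 0.95 at Day 8. For nominal Day 7 data to cover one half-life, it would have to be 144 h or less, 20% below the stated 180 h ((180 − 144)/180 = 0.20).

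**The case against.** The best defence is that Section 3.4 speaks of safety data in general and does not promise that every assessment is repeated after 180 h. Adverse events and vital signs are scheduled at 216 h nominally, and five of the eight criteria in Section 3.7 (similar signs or symptoms, related serious events, severe events, tachycardia, hypertension) rest on such data. That stands, and it rules out the stronger reading a reader might infer, that the Part A review as a whole falls short of one half-life or that the stopping criteria cannot be applied. They can be applied. The liver-test and QTcF criteria are simply judged on shorter follow-up than the text implies.

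A second tempting reading is that nobody's laboratory or ECG data go beyond 144 h. The documents do not support that either. The stagger may give the first one or two subjects later results, Section 3.6 calls for all available data, and a Day 7 visit held on Day 9 reaches 192 h. But none of this is required, and the remaining 2 of 4 or 6 of 8 subjects still depend on the Day 7 visit. The cumulative review adds groups at lower doses, not later data from the group just dosed. The archived continuous ECG does not fill the gap: it ends at 24 h and is not available for review during the study (Appendix 6, footnote c).

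Third, Section 3.6 fixes the cut-off at 216 h, events can be reported spontaneously at any time, and 180 h is only approximate, so 0.93 of a half-life is a small miss at the edge of a window. All fair. The window point is the lesser one; it matters because Section 3.4 claims to ensure the coverage. Sections 7.3 and 7.3.2 allow extra or adjusted assessments, but at discretion. The wide predicted exposure margins in Section 3.5.2 lower the likely risk without making the sentence true.

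**Conclusion.** The coverage stated in Section 3.4 holds nominally for adverse events, concomitant medication and vital signs (216 h, 1.2 half-lives). It does not hold for laboratory tests, 12-lead ECG, injection-site assessment or symptom-directed examination, which nominally end at 144 h (0.80 half-life; 96 to 192 h, or 0.53 to 1.07, across the window) for 2 of 4 or 6 of 8 subjects in each group. Nor is it ensured for the Day 10 visit itself, which is in window at 168 h (0.93).

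A reader might carry the laboratory and ECG gap over to Part B. That would be wrong: the Day 22 visit there includes laboratory tests, ECG and injection-site assessment. Only the window point applies, with Day 20 at 168 h after the final dose.

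The conclusion takes the half-life at 180 h and visits on their scheduled days. It is unchanged at 176 h. It concerns a stated property of the review that the schedule does not deliver, and it makes no claim about which follow-up is clinically adequate.

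**What to change.** The sponsor must reconcile Sections 3.4 and 3.6 with the Part A schedule and the visit windows in Appendix 6. After that, one of two things should be true. Either the stated half-life coverage holds for the data that the liver-test and QTcF criteria use, or the text gives the actual coverage by data type: 216 h nominal (1.2 half-lives) for adverse events and vital signs, and 144 h nominal (about 0.8 half-life) for laboratory and ECG data. The ±2-day window should be addressed in the same step, for Part B Day 22 as well. Which passage to change is for the sponsor to decide.

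Changing the text costs nothing in assessments. For scale if the schedule is changed instead, a Part A laboratory sample is 7.5 mL against a planned total of 124.5 mL (Appendix 3).

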3.4.2. Pharmacodynamic Assessment

Pharmacodynamic assessments will be conducted for subjects in Groups A2, A4, and A6.

Human experimental pain models using healthy volunteers can be used to assess the effect of a drug or treatment under controlled clinical conditions. Capsaicin is a vanilloid responsible for the pungent taste of hot peppers. In mammalian species, capsaicin-induced pain is mediated through Group C nerve fibers following activation of vanilloid 1 transient receptor potential (TRPV1) channels⁵. $Na_v1.7$ has been implicated in controlling neuropeptide release from C-fibers, and suppression of capsaicin-induced neurogenic flair has been demonstrated by an $NA_v1.7$ inhibitor⁶.

Several studies have used intradermal capsaicin for human experimental pain studies^{7,8}. It has been possible to demonstrate dose-dependent responses, with intradermal injections of 100 µg generally agreed to be the ideal dosage for these studies. Intradermal injection of capsaicin causes a brief stinging/burning pain at the injection site (spontaneous pain) followed by development of secondary hyperalgesia, which can be assessed using equipment such as Von Frey hairs. A study by Gazerani et al.⁵ found that the response was site-specific and while peak pain intensity and duration were greatest in the forehead it was found that areas of visible flare and secondary hyperalgesia were significantly larger in the forearm, making the forearm the most suitable site for experimentation.

Covance CRU, Leeds, UK in 2009 performed a validation study using intradermal capsaicin (Covance CRU Study: 9999-004) with between-subject and within-subject variability demonstrating that the assessments can be reliably conducted to assess pharmacological response.

For these reasons, it has been decided to:

- Measure both capsaicin-evoked pain and secondary hyperalgesia.
- Limit the number of capsaicin tests to 3 for each subject (pre-screening, baseline, and 48 hours postdose)
- Exclude subjects who have pain <3 or >9 (using a Visual Analogic Scale [VAS]) at the pre-screening visit from PD assessment groups.

3.5. Selection of Doses in the Study

3.5.1. Starting Dose

The rat has been identified as the most sensitive species in a 13-week SC toxicity study with a 4-week recovery phase (Covance study no. 8355564). The NOAEL was the 100 nmol/kg/dose (462.29 µg/kg/dose). This dose level resulted in C_{max} of 27.6 ng/mL and 24.9 ng/mL in males and females, respectively, and AUC_{0-24} of 174 ng.h/mL and 128 ng.h/mL in males and females, respectively⁴. As the exposure was lower in the female rats these data have been used to calculate the safety margins.

The dose of 462.29 µg/kg/dose corresponds to human equivalent doses (HEDs) of 74.8 µg/kg/dose, which gives a maximum recommended starting dose (MRSD) of 444 µg for a 60-kg human and thus a 15000-fold safety margin to the proposed starting dose of 30 ng and 22-fold margin to the proposed maximum dose of 20 µg. Additionally the NOAEL dose in the cynomolgus monkey was identified as 100 nmol/kg/dose (462.29 µg/kg/dose), which gives a higher HED of 150 µg/kg/dose.

In vivo, doses of 10 pmol/kg/dose (0.0462µg/kg/dose) or less were found to inhibit peripheral acute inflammatory pain. The equivalent human dose for a 60-kg human is 44 ng, thus a dose at which minimal biological effect is anticipated has been selected as the starting dose of 30 ng.

